# ABBREVIATIONS AND DEFINITIONS OF TERMS

NCI	National Cancer Institute
PeRC	Pediatric Research Consortium
WTH	Way to Health Platform
EHR	Electronic Health Record
DBHi	Department of Biomedical and Health Informatics

#### ABSTRACT

#### Context:

Cigarette smoking remains a leading preventable cause of death in the US with substantial morbidity, mortality, and financial costs each year. More than 90% of adult smokers initiate tobacco use before age 18, making prevention and treatment of adolescent smoking a critical health priority. Behavioral economic interventions utilizing financial incentives can promote smoking cessation in adult populations. No studies have evaluated financial incentives among adolescents to promote engagement in effective smoking cessation programs through primary care settings.

#### Objectives:

**Primary Objective:** To compare, through a pilot, randomized controlled trial, an intervention incentivizing contact with the Quitline, an intervention incentivizing quitting, or no financial incentive intervention on adolescent smoker enrollment and depth of engagement in a smoking cessation program (Free Smoker Quitline).

**Secondary Objective:** To compare cotinine-confirmed 2-month quit rates across the 3 groups, among users who report abstinence.

#### Study Design:

This is a randomized controlled trial of a quitline incentive vs smoking cessation incentive vs no financial incentive on adolescent engagement with a smoking cessation program.

#### Setting/Participants:

Setting: Primary care sites within CHOP's Pediatric Research Consortium along with other nonclinical community settings.

[figure not shown]
60 adolescent smokers will be recruited. Eligibility criteria include adolescents (aged 14-21 years), who speak English, live in Pennsylvania, screen positive for tobacco use, are interested in quitting, and have a smart phone.

#### Study Interventions and Measures:

Adolescents will be randomized to 1 of 3 financial incentive groups: (1) Quitline Incentive: the payment structure emphasizes engaging with the quitline, with an additional smaller payment for smoking cessation; (2) Smoking Cessation Incentive: the payment structure emphasizes quitting regardless of engagement with the quitline (though the quitline will be presented as a helpful tool); and (3) no financial incentive. The Quitline is funded by the Pennsylvania Department of Health and staffed by trained cessation counselors available 24 hours a day, 7 days a week.

**Outcomes Measures:** Objective 1: The main outcome of interest is adolescent smoker completion of the smoking cessation program, defined as the proportion of smokers identified in the clinic that enroll, use, and complete the Quitline program compared across the 3 groups. Objective 2: The secondary outcome is to confirm abstinence, via salivary cotinine concentration of <30 ng per milliliter at 10 weeks after the start of the study.

#### **FIGURE 1: STUDY DIAGRAM**

### **1 BACKGROUND INFORMATION AND RATIONALE**

#### 1.1 Introduction

Cigarette smoking remains a leading preventable cause of death in the US with substantial morbidity, mortality, and financial costs each year. Nearly 20% of US adolescents smoke cigarettes or use other tobacco products like e-cigarettes, 80% of youth who initiate smoking transition to regular use by young adulthood, and more than 90% of adult smokers initiate tobacco use before age 18, making prevention and treatment of adolescent smoking a critical health priority. Further, e-cigarettes are now the most common tobacco product used by teenagers, and adolescent use of e-cigarettes is strongly associated with transition to cigarette use. Pediatricians see the majority of the US child and adolescent population, and adolescents view pediatricians as trusted sources for credible health information. Consequently, pediatricians are uniquely positioned to screen for tobacco use in their patients, initiate treatment, and connect adolescents to smoking cessation services.

While evidence-based smoking cessation programs for adolescent tobacco use are available, including the quitline, text messaging, mobile phone apps and web-based programs, they are underutilized by teenagers. Although most youth smokers want and attempt to quit, few seek assistance to do so. Consensus guidelines and the US Preventive Service Task force emphasize that clinician counseling can initiate behavior change in adolescent tobacco users and effectively educate them about available smoking cessation resources. A critical knowledge gap is how to best to translate screening into effective service receipt and quitting.

Behavioral economics applies economic, marketing and psychological principles, such as framing, present bias, and loss aversion, to overcome barriers to behavior change. Behavioral economic interventions utilizing financial incentives have been used to promote smoking cessation in adult populations. Among adolescents, a systematic review of financial incentives for smoking cessation suggests potential for promoting abstinence. To our knowledge, no studies have evaluated use of financial incentives among adolescents to promote engagement in effective smoking cessation programs through pediatric healthcare settings.

### 1.2 Name and Description of Intervention

Way to Health (WTH) Platform: Way to Health is a web-based platform that automates many of the research functions necessary for conducting randomized controlled trials of healthy behavior interventions. This was designed by faculty and staff at the LDI Center for Health Incentives and Behavioral Economics (CHIBE) at the University of Pennsylvania to create an efficient, scalable, and low-cost way to test behavioral interventions using a platform that can be deployed anywhere in the United States. The WTH platform uses secure, high-performance servers that have the necessary security protections to permit storage and analysis of data containing protected health information. Further, the WTH platform has secure financial tracking and processing systems to manage participant payments, including the ability to track earnings and pay participants via a non-integrated payment system (ClinCard) ideally suited for adolescent subjects.

### 2 STUDY OBJECTIVES

The purpose of the study is to determine if financial incentives for adolescent smokers compared to no financial incentive increases engagement in a smoking cessation program.

#### 2.1 Primary Objective (or Aim)

The primary objective of this study is to compare, through a pilot, randomized controlled trial, an incentive for Quitline engagement, an incentive for smoking cessation, or no financial incentive intervention on adolescent smoker enrollment and depth of engagement in a smoking cessation program (Free Smoker Quitline, hereafter referred to as the Quitline).

### 2.2 Secondary Objectives (or Aim)

The secondary objective is to compare cotinine-confirmed 2-month quit rates across the 3 groups, among users who report abstinence at the 10-week follow-up call.

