### 3.1.3 Follow-up Phase

To be eligible for the follow-up phase, adolescents must self-report tobacco cessation. All study subjects will be contacted by the study team 10 weeks after study enrollment to inquire about smoking cessation (defined as no tobacco use in the last 30 days). For subjects that report quitting, to confirm cessation, subjects will complete a salivary cotinine specimen. The result will either be collected at the clinic or collected remotely, in the latter case performed in front of a live video-conference with a study staff member to confirm adherence. The result can be reported immediately.

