## 3.3.2 Total Number of Study Sites/Total Number of Subjects Projected

The study will be conducted at primary care sites within CHOP's Pediatric Research Consortium (PeRC). Subjects may also be recruited through study materials distributed at up to 2 schools and posted in up to 10 other non-clinical community settings (for example, a commercial entity like convenience stores). Permission will be obtained from the school principle or non-clinical community setting building owner/proprietor before any recruitment materials are distributed.

Recruitment will stop when approximately 60 subjects are enrolled. It is expected that approximately 70 subjects will be enrolled to produce 60 evaluable subjects.

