#### 6.3.2 Efficacy Analysis

We will calculate proportions for the clinical outcomes (enrollment, use, and completion of the Quitline program) and evaluate the magnitude and statistical significance of differences between the 3 groups. Intention-to-treat analysis will be used so that subjects will be analyzed according to the group to which they were initially randomized. Secondary analyses will describe results for participants as-treated. Categorical variables will be compared between groups using chi-square tests. Multivariable logistic regression models (that potentially include confounding variables) will be used to compare quit rate between groups. These models will include indicator variables for each of the financial incentive groups; the no financial incentive group will be the reference. The treatment groups will differ significantly from usual care if its indicator variable differs significantly from zero (p-value < 0.05 as criterion for statistical significance in a likelihood ratio or Wald's test). A Wald's test of the hypothesis that the two indicator variables are equal will also be performed (hypothesis that the probability of a subject quitting is the same for both financial incentive groups). We will explore for potential confounding by referral bonuses in the models and adjust if necessary.

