#### 7 STUDY INTERVENTION

#### 7.1 Description

Intervention: Subjects will be randomized within the WTH platform to 1 of 3 financial incentive groups:

- 1) Quitline Incentive: the payment structure emphasizes engaging with the quitline, with an additional smaller payment for smoking cessation. Each adolescent can receive \$15 payments for enrolling in the quitline, for maintaining involvement in the quitline program (\$15 per call for up to 5 calls), and, for those reporting abstinence, \$20 for submitting the cotinine swab and \$25 for confirmed quitting (negative cotinine swab);
- 2) Smoking Cessation Incentive: the payment structure emphasizes quitting regardless of engagement with the quitline (though the quitline will be presented as a helpful tool). Each adolescent will receive \$15 for enrolling in the quitline and, for those reporting abstinence, \$20 for submitting the cotinine swab and \$100 for confirmed quitting (negative cotinine swab); and
- 3) No financial incentive.

The WTH platform has secure financial tracking and processing systems to manage participant payments, including the ability to track earnings and pay participants via a nonintegrated payment system (ClinCard) ideally suited for adolescent subjects. ClinCards are reloadable, prepaid cards managed by Greenphire. Subjects will be able to access the payments during the study duration. Payments are based off the following:

- Enrolling in the Quitline Program, defined as the subject connecting with a Quitline counselor, providing basic information about smoking history, and discussing program details (see "Quitline Delivered Treatment" section below). To receive this payment, subjects must enroll in the Quitline within 2 weeks of start of the study;
- Maintaining involvement in the program, defined as the subject engaging in 5 proactive counseling calls with the Quitline counselors. Calls are scheduled every 1-2 weeks, depending upon the needs of the subject, and the Quitline counselor reaches out to the subject to initiate the call. Subjects eligible to receive payments for quitline calls must complete each call within a 2-week designated window;
- **Submitting the Cotinine Swab,** defined as, for those subjects who self-report quitting smoking (defined as no tobacco use in past 30 days) at the 10-week follow-up call, successfully completing the cotinine-specimen within 2 weeks of the call.

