- **Quit Confirmed**, defined as a salivary cotinine measurement concentration of <30 ng per milliliter.

Subject engagement with the Quitline will be reported back to the WTH platform in real time using secure, password-protected methods. This allows subjects, through their interactions with the WTH platform, to see regular progress reports of their payments. See Table 1 for payment structure.

All subjects across the 3 groups, regardless of their level of engagement with the Quitline, will be contacted by the study team at 10 weeks after study enrollment to assess their smoking status. For those reporting quitting smoking, they will be asked to complete the salivary cotinine measurement.

Table 1: Payment Structure									
	Connect to Way to Health	Quitline Enrollment	Quitline Counseling Calls			Submit Cotinine Swab*	Quit Confirmed ^		
Incentive, Quitline	\$15	\$15	\$15	\$15	\$15	\$15	\$15	\$20	\$25
Incentive, Smoking Cessation	\$15	\$15	0	0	0	0	0	\$20	\$100
No Incentive	\$15	0	0	0	0	0	0	\$20	0

\*For subjects that report quitting smoking (defined as no tobacco use in past 30 days) at the 10-week followup call. All subjects will receive \$20 for submitting the salivary cotinine swab, regardless of the result. ^Payment received for negative result, meaning cotinine level <30 ng per milliliter

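### The secondary objective compares confirmed quit rates only among subjects who report abstinence, a subset formed after randomisation, and no section fixes the denominator

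*Combined protocol and SAP*

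**What the plan says.** The restriction appears twice. The abstract (Objectives) has "To compare cotinine-confirmed 2-month quit rates across the 3 groups, among users who report abstinence", and section 2.2 has "compare cotinine-confirmed 2-month quit rates across the 3 groups, among users who report abstinence at the 10-week follow-up call".

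Section 6.3.2 reads differently. It compares quit rates in a logistic model without naming a subset, and it tests the "hypothesis that the probability of a subject quitting is the same for both financial incentive groups". Its intention-to-treat statement is that "subjects will be analyzed according to the group to which they were initially randomized".

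The endpoint text (abstract Outcomes Measures, 5.2 and 6.2) gives the cotinine threshold of 30 ng/mL at 10 weeks and no denominator. Sections 3.1.3 and 7.1 have every subject contacted at 10 weeks, but only some swabbed: "To be eligible for the follow-up phase, adolescents must self-report tobacco cessation" (3.1.3) and "For those reporting quitting smoking, they will be asked to complete the salivary cotinine measurement" (7.1). To earn the swab payment, the specimen must be given within 2 weeks of the call (7.1).

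Section 3.3.2 introduces a further set that it does not define: "It is expected that approximately 70 subjects will be enrolled to produce 60 evaluable subjects". No section says how to count subjects who report tobacco use, are not reached, or report abstinence without giving a swab.

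**The concern.** Reporting abstinence at week 10 happens after randomisation and is something the incentives are meant to change. A comparison confined to reporters is therefore not protected by randomisation, and it answers a different question: of those who say they quit, how many does the swab confirm? Subjects who report use or are not reached drop out of the denominator, although they belong in a quit rate.

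Section 6.4 gives estimation of effect size for a future larger study as a goal of the pilot. A confirmation rate carried forward as a quit rate would mislead that planning, and it would rest on a handful of subjects per arm. An analyst following these documents could defend at least three denominators: reporters, the evaluable set, or all randomised.

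**Working it through.** **Plan's own figures.** Only 3 × 20 = 60 can be reproduced, and it agrees. Section 6.4 makes no formal calculation, and no quit, reporting or swab-completion rate is stated. The rates below are therefore assumptions.

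**Set-up.** n = 20 per arm (6.4). True quitting q is 20% in one incentive arm and 10% with no incentive. All quitters report abstinence. A share f of non-quitters reports it falsely and fails the swab. A share s of quitters completes the swab, and a reporter without a swab stays in as not confirmed.

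- Literal rate = q·s / (q + (1 − q)·f)
- All-randomised rate = q·s
- Expected literal denominator = 20·(q + (1 − q)·f)

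**1. No false reporting, full swab completion (f = 0, s = 1).** Literal: 0.20/0.20 = 100% against 0.10/0.10 = 100%. All randomised: 20% against 10%. The literal rate is undefined if an arm has no reporter: 1 − (1 − 0.8^20)(1 − 0.9^20) = 13.2% of trials. For at least one of three arms, both incentive arms at 20%: 1 − (1 − 0.8^20)²(1 − 0.9^20) = 14.2%.

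**2. Equal false reporting in both arms (s = 1), by exact enumeration.** The wrong-direction column is the chance that the better arm shows the lower rate; for the literal rate it is taken over trials where that rate is defined. No finite odds ratio means that an arm has no reporter, none confirmed, or all confirmed (unadjusted logistic model, incentive against none).

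| f | Literal rate, incentive vs none | Expected denominators | Wrong direction | No finite odds ratio |
|---|---|---|---|---|
| 2.8% | 89.9% vs 79.9% | 4.4 and 2.5 | 23.6% | 87.5% |
| 5% | 83.3% vs 69.0% | 4.8 and 2.9 | 27.3% | 71.2% |
| 10% | 71.4% vs 52.6% | 5.6 and 3.8 | 26.0% | 40.6% |
| 15% | 62.5% vs 42.6% | 6.4 and 4.7 | 23.7% | 24.5% |
| 30% | 45.5% vs 27.0% | 8.8 and 7.4 | 20.5% | 13.7% |
| All randomised, any f | 20% vs 10% | 20 and 20 | 12.8% | 13.2% |

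Over this range the literal difference is 10 to 20 points and keeps its direction on average. Between f = 0 and 2.8% it rises from 0 to 10 points. At f = 0 no trial gives a finite odds ratio.

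**3. When would the direction reverse on average?** Setting the two literal rates equal gives f₁/f₀ = (0.9/0.1) × (0.2/0.8) = 2.25. False reporting in the incentive arm would have to exceed 2.25 times that in the control arm. The documents do not imply this.

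**4. Swab completion (f = 0).**
- Completion 80% in both arms: literal 80% against 80%; all randomised 0.20 × 0.80 = 16% against 0.10 × 0.80 = 8%.
- Equal true quitting of 20%, completion 95% against 60%: literal 95% against 60%, a spurious 35 points; all randomised 19% against 12%, a spurious 7 points. Counting reporters without a swab as quit gives 20% against 20%.

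**5. Evaluable set.** Four confirmed quitters are 4/20 = 20.0% of an evaluable arm, but 4/(70/3) = 4/23.3 = 17.1% of an enrolled arm.

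**The case against.** The strongest reply is that the phrase only describes who is swabbed. All subjects are called and reporters are then verified, so the objective can be read as loose wording for that procedure. Section 6.3.2, the only analysis text, names no subset and speaks of the probability that a subject quits. The model failures shown above themselves suggest that nobody intended a logistic regression on so few reporters. This reading is plausible. But no section states it, and the objective attaches the restriction to the comparison itself, in two places. The intention-to-treat sentence does not settle the matter, because a subset can also be analysed by assigned arm.

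Second, the figures rest on assumptions, and 100% against 100% is an idealised corner. That is right. They show how the literal measure behaves and do not forecast this trial.

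Third, differing swab completion is hypothetical, since Table 1 pays $20 for the swab in every arm, and an all-randomised denominator does not cure it. Both parts stand. Payment for a negative result does differ ($25, $100 or $0), so a difference is possible and worth examining.

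Fourth, this is a secondary objective of a pilot, the worst-case sensitivity analysis is optional at 20 per arm, and nothing ties the evaluable set to the quit rate. This bears on weight and on the extras, not on the need to name a denominator.

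**Conclusion.** The concern holds. The objective as written specifies a measure that is not a quit rate, section 6.3.2 points to another, and nothing reconciles them. It is a conflict to resolve, not proof that the wrong analysis will be run.

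Under the stated assumptions, a true difference of 10 points appears as 0 with honest reporting and full swab completion. With equal false reporting of 2.8% to 30%, it appears as 10 to 20 points, on expected denominators of 2.5 to 8.8 instead of 20, and the better arm looks worse in 21% to 27% of defined trials against 13% with all randomised. The argument about the denominator does not depend on these rates; its size does. The primary Quitline outcome is not affected. The text should be corrected before the quit-rate results are seen.

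**What to change.** In the abstract, 2.2, 6.2 and 6.3.2:

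- Define the quit rate as subjects with self-reported 30-day abstinence at the 10-week call and cotinine below 30 ng/mL, divided by all subjects randomised to the arm. State that the evaluable set of 3.3.2 is not the denominator.
- Fit the 6.3.2 logistic model on all randomised subjects. Count as not confirmed those who report use, are not reached, or report abstinence without a swab.
- Report by arm the number not reached and the number reporting abstinence without a swab.
- Add a sensitivity analysis for these two groups only: (i) count reporters without a swab as quit in every arm; (ii) as a worst case, count both groups as quit in the no-incentive arm only. Subjects who report use stay as not quit throughout.
- Report the confirmed share of self-reports by arm as descriptive only.
- Say whether the 2-month label names the assessment time or the length of abstinence.

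The cost is wording in four places and one added analysis. No new data are needed, because all subjects are already contacted at 10 weeks. The quit proportions will be numerically lower, and bias from unequal swab completion is reduced but not removed.

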### **3 INVESTIGATIONAL PLAN**

### 3.1 General Schema of Study Design

This is a randomized controlled trial of financial incentives on adolescent engagement with a smoking cessation program (Quitline).

#### 3.1.1 Screening Phase

Potential adolescent subjects will be screened using the protocol inclusion and exclusion criteria. Adolescent smokers may be identified at their primary care visit through standard screening approaches embedded within the electronic health record (EHR) (Epic®) at PeRC study sites. Adolescent smokers may also be identified through outreach facilitated by the CHOP Research Enhancement Core (REC).

Adolescents will be recruited in one of three ways:

- 1. Adolescents who screen positive for tobacco use at their primary care visit (defined as having smoked cigarette(s) and/or used an e-cigarette on at least 1 day during the 30 days before the clinical encounter) and are interested in treatment will be approached over the phone (with a potential introductory text message) by the study team to gauge interest in participating and obtain consent either electronically or over the phone and confirm participant eligibility.
- 2. Adolescents who contact the study team as a result of outreach facilitated by the REC will be screened by the study team. The team will describe the study, inform prospective participants of the eligibility requirements, and ask the prospective participants if they are still interested in participating. If interested, the study team will obtain consent either electronically or over the phone and confirm participant eligibility.
- 3. Facilitated by REC, advertisements with study information, including eligibility requirements and an embedded REDCap link, will be distributed at schools, CHOP

primary care clinics, and other non-clinical community settings (for example, a commercial entity like convenience stores). Adolescents who are interested in learning more can go to the REDCap link where they will provide consent electronically and then be screened for eligibility. Permission will be obtained from the school principle or non-clinical community setting building owner/proprietor before any recruitment materials are distributed. The research presents minimal risk to participants and involves no procedures for which written consent is normally required outside of the research context.

